COVER PAGE

NCT06079853

Date of Protocol Approval: 10/18/2023

Study Title: The Use of Physiologic Measures and Sleep Health Promotion to Identify and Mitigate Predisposing Factors of Suicidal Ideation in Nurses

PI: [name], RN, ANP-BC, FAAN

PI Contact: [contact]

Sponsor: Columbia University School of Nursing

STUDY PROTOCOL

The purpose of this study is to generate longitudinal pilot data that investigates 1) which factors (stressful life events, psychiatric characteristics, and work environment characteristics) are associated with stress and subsequent suicidal ideation; and 2) to explore the preliminary impact of an existing evidence-based sleep intervention, *Somni*^{®14}, on stress, psychological health, and suicidal ideation in working nursing professionals. The specific aims are:

Aim 1. To investigate associations between sleep, stressful life events (life stressors, discrimination, lateral violence), psychiatric characteristics (psychiatric diagnosis, subjective mood), work environment characteristics (workload, shift type and duration, overtime, nurse work environment, and team relations) and stress (self-reported and heart rate variability) in working nursing professionals while controlling for standard covariates known to influence stress. *Hypothesis 1:* Suboptimal work environment characteristics are positively associated with self-report and physiologic indicators of stress [heart rate variability (HRV)]. *Hypothesis 2:* Poor sleep (duration and quality) will be positively associated with self-report and physiologic indicators of stress (HRV).

Aim 2. To determine if stress exposure (self-report and HRV) are associated with predisposing factors (sleep, stressful life events, additional psychiatric characteristics, and work environment characteristics), and to explore whether stress mediates the effect of predisposing factors on suicidal ideation in working nursing professionals. *Hypothesis:* Nurses with low HRV are at higher risk for suicidal behavior when exposed to poor sleep, the presence of psychiatric characteristics (e.g. Depression), stressful life events, or suboptimal work environment characteristics (e.g., poor team relations).

Exploratory Aim. To explore the preliminary impact of an existing sleep intervention (*Somni*[®]) on self-reported stress, HRV, sleep, and psychiatric health outcomes including depression, burnout, and suicidal ideation.

STUDY DESIGN. This study is a prospective pragmatic pilot trial to generate data needed to inform a fully-powered longitudinal study consisting of nurses across a wider geographic region. There are 4 study components:

1. Electronic Quantitative Surveys (baseline, Week 4 & Week 8) will consist of demographic questions and validated measures for personal characteristics, sleep, stressful life events, psychiatric characteristics, work environment factors, and all psychological health outcomes. (**Table 1**). The surveys will be administered 3 times (baseline, week 4 and week 8) to generate pilot longitudinal data.

2. Psychological Assessment (baseline). To confirm a preexisting psychiatric diagnosis, a *Structured Clinical interview for DSM-5 Diagnosis* (Research version) (SCID-5-RV) will be administered in-person by a Psychiatric Mental Health Nurse Practitioner (PMHNP) at baseline. SCID-5-RV is a semi-structured interview guide for making major DSM-5 diagnoses such as mood disorders, psychotic symptoms, substance use, sleep, and trauma- or stressor-related disorders and takes approximately 45-60 minutes to administer. Studies suggest that prior history of mental illness, such as depression, has been linked to suicide.

3. Physiologic Biomarkers (Weeks 1-8). Heart rate and sleep (hours/day) will be collected using a wearable device, *Oura ring*[®], a piece of jewelry that can be custom fit to each participant. Heart rate variability (HRV), a highly sensitive physiologic metric for stress, is the constant variation in milliseconds between beats, and controlled by the autonomic nervous system. Low HRV is a strong indicator of physiologic stress (fight or flight response) and has been associated with increased risk for suicide attempt. Studies have demonstrated high validity in the assessment of HRV and sleep using the *Oura ring*[®]. The device will also collect activity levels (steps/day) and sleep cycles, known confounders for stress levels.

TABLE 1. Study Variables and Measures

Variable	Operational Definition	Measure
Demographics	Age, Sex, Gender, Race, Ethnicity, marital status, household income, parental status, smoking history, substance use; years of nursing experience	Validated single-items
Sleep	Sleep quality and duration	Pittsburgh Sleep Quality Index ⁴⁴ ($\alpha = .83$) Oura ring [®] Somni [®] 14
Stress	Self-reported stress Heart Rate Variability	Perceived Stress Scale ⁴⁵ ($\alpha = .76$) Oura ring [®]
Suicidal Ideation	Suicidal Ideation	Columbia-Suicide Severity Rating Scale ⁴⁶ ($\alpha = .94$)
Stressful Life Events		
Life Stressors	43-item checklist to assess changes in life (e.g. divorce; death of friend)	Holmes & Rahe Stress Scale ⁴⁷
Discrimination	Perceived discrimination	Perceived Discrimination Scale ⁴⁸ ($\alpha = .93$)
Lateral Violence	Bullying/incivility	Negative Acts Questionnaire-Revised ⁴⁹ ($\alpha = .90$)
Psychiatric Characteristics		
Psychiatric Diagnosis	Psychiatric Diagnosis	SCID-5-RV (Research Version) ⁴²
Subjective Mood	Depression Burnout	Beck's Depression Index-II ⁵⁰ ($\alpha = .91$) Maslach Burnout Inventory-HSS ⁵¹ ($\alpha = .91$)
Work Environment Characteristics		
Workload	Perceived workload Overtime RN-patient staffing ratio	NASA Task Load Index ⁵² ($\alpha = .80$) Self-reported number of hours Standard ratio; frequency of shifts above standard
Shift Work	Shift type (day or night shift) Shift duration (hours)	Validated single-items Self-reported mean hours/shift Number of quarterly overtime hours
Practice Environment	Nurse Participation; quality of care; management and leadership; human resources; nurse-physician relations	Practice Environment Scale-Nursing Work Index ⁷ ($\alpha = .80$)
Team Relations	Clinician team cohesiveness	Provider Co-management Index ²⁷ ($\alpha = .96$)

4. Sleep Intervention (Weeks 4-8) *Somni*[®] is an evidence-based personalized sleep intervention aimed at promoting optimal sleep health and has demonstrated effectiveness in shift workers outside the healthcare sector (e.g. Disney). *Somni*[®] consists of a sleep kit and a smart phone application. The sleep kit is box of items with demonstrated past evidence of improving sleep health: Blue light blocking glasses, white noise machine, lavender spray, ear plugs, light blocking eye mask, and herbal tea. Rather than dictate a “one size fits all” approach to optimize sleep health, there is current evidence that individualized sleep interventions are recommended to optimize sleep quality. *Somni*[®] permits individualized sleep quality promotion and participants are able to select their preferred use, timing, and duration of each of the box contents. The kit is accompanied by a *Somni*[®] smartphone app that prompts participants to input the use of each component in the kit and provide a subjective sleep quality rating each day. Drs. [name] and [name] have partnered with the developers of *Somni*[®] who will provide free sleep kits and app access to our study participants. The *Somni*[®] app is interoperable with the *Oura Ring*[®] and will automatically sync all physiologic and sleep data together in one location, fully accessible to the participants, and displayed in graphs in the *Somni*[®] app that are easy to read and interpret (e.g. total daily steps; daily sleep hours). *Somni*[®] will be implemented Weeks 4 through 8 to investigate its preliminary impact on stress and suicidal ideation by comparing survey and physiologic metrics from Weeks 1-4.

STATISTICAL ANALYSIS

First, we will calculate composite scores of individual measures (sleep, stressful life events, psychiatric characteristics, and work environment characteristics). Descriptive statistics will be calculated including means

and standard deviations (normally distributed values), median and interquartile range (non- normally distributed variables), or absolute and relative frequencies (categorical variables). Outliers and missing data will be assessed (outliers > 3 standard deviations from the mean will be removed). Significance level will be set at $\alpha = 0.05$.

Aim 1. We will calculate bivariate Pearson or Spearman's rank order correlation coefficients as well as simple linear regression and univariate ANOVAs. We will use linear mixed models to examine the relationships between individual and composite scores of factors (sleep, stressful life events; psychiatric characteristics; work environment characteristics) and 1) self-report stress and 2) HRV, while controlling for personal characteristics (age, sex, highest degree earned, years of experience, years of practice in current environment, smoking status). We propose the following model to test all hypotheses:

$Y_g[E(i)] = \beta_0 + \beta_1 X_i + \beta_2 F$ where Y_g represents the outcomes measure (self-report and HRV separately) for each participant i . X_i are the individual-level covariates (e.g., sex, gender, race, age, mental health history), F represents each job stressor and work environment variable. As the primary outcome is stress (mean score and mean HRV), possible distributions such as Poisson, zero-truncated Poisson, negative binomial, or zero-truncated negative binomial will be assessed to determine the best fit link function.

Aim 2. We will classify nurses into quartiles of high (top 25%), medium (middle 50%), and low (bottom 25%) HRV. We will use descriptive statistics to examine individual measures and composite scores of factors (sleep, stressful life events, psychiatric characteristics, work environment characteristics) and suicidal behavior [C-SSRS score]. To evaluate the change in suicidal ideation over time and the impact of each factor composite score, we will fit conditional latent growth curve models using 3 data points. The models will be expressed such that, given mean HRV and baseline composite scores for each factor category: $y_{it} = (\mu_a + \mu_\beta \lambda_t + \gamma_1 HCC_i + \gamma_2 WEC_i) + (\zeta_{ai} + \zeta_{\beta i} \lambda_t) + \varepsilon_{it}$ where y_{it} is the C-SSRS score for nurse i at time t , μ_a is the latent variable for the intercept value (baseline score), μ_β is the random latent variable for slope (growth over time) for nurse i multiplied by the vector of factor loadings specifying time, λ_{it} , ε_{it} is the time-specific residual for nurse i , ζ_{ai} and $\zeta_{\beta i} \lambda_t$ are random components of the latent intercept and slope variables, respectively. Sleep, stressful life events and psychiatric characteristics are fixed (time-invariant) predictors. The factor loadings for time on slope can be fixed to adjust for gaps in outcomes, which would allow for modeling more distant (e.g., 2025) data from baseline without increasing the number of timepoints included in the model. Further, we anticipate fluctuations in HRV over time. To accommodate the change in trend, we will explore both linear and quadratic growth functions. Baseline global sleep scores (PSQI), stressful life events, psychiatric and work environment characteristics will serve as predictors of suicidal ideation change over time. Individual nurse characteristics and psychiatric characteristic controls will be included as an interaction term to compare curves across nurses. To explore whether stress mediates the effect of predisposing factors on suicidal ideation, we will compare the models assessing the effect of predisposing factors on suicidal ideation with and without the mediator outlined by Barron and Kenny difference method which be used to gauge the size of the mediation effect.

Aim 3. We will calculate descriptive statistics, percentages, and frequencies for 1) each *Somni*[®] sleep kit component 2) subjective sleep quality via *Somni*[®] app 3) global sleep scores (PSQI score) and HRV. We will test differences in global sleep scores (PSQI), mean sleep duration (Oura ring), mean subjective sleep quality and use of sleep kit components at the individual level between the 3 data points. We will report the effect sizes and will test for significance in the model for each psychosocial and work environment factor, each *Somni*[®] sleep kit component (mean weekly frequency), and the mean PSQI score while controlling for age, sex, gender, race, and history of psychiatric diagnosis. We will repeat the same analysis modeling mean C-SSRS as the dependent variable. To evaluate the change in suicidal behavior over time and the impact of global sleep (PSQI score) and each *Somni*[®] sleep kit component (mean weekly frequency), we will fit conditional latent growth curve models.

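### Steps/day is called a known confounder for stress, yet no covariate list for the Aim 1 stress and HRV models names it

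*Combined protocol and SAP*

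**What the plan says.** The ring component of the Study Design is headed "3. Physiologic Biomarkers (Weeks 1-8", so activity is available for the whole study period. Of the ring's further outputs it says: "The device will also collect activity levels (steps/day) and sleep cycles, known confounders for stress levels".

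The statement of Aim 1 promises to examine stress, both self-reported and HRV, "while controlling for standard covariates known to influence stress".

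The Aim 1 paragraph of the Statistical Analysis describes the adjustment in two ways. The linear mixed models are to be fitted "while controlling for personal characteristics (age, sex, highest degree earned, years of experience, years of practice in current environment, smoking status"). The equation that follows says "X_i are the individual-level covariates (e.g., sex, gender, race, age, mental health history") and "F represents each job stressor and work environment variable".

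The later aims have their own controls. For Aim 2: "Individual nurse characteristics and psychiatric characteristic controls will be included as an interaction term to compare curves across nurses". For Aim 3: "while controlling for age, sex, gender, race, and history of psychiatric diagnosis".

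The only other mention of steps is in the Somni component, where daily steps are an example of what the app shows to participants.

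**The concern.** By the protocol's own account, steps/day is the kind of variable that Aim 1 undertakes to control for, and it is already being recorded. The analysis text gives it no role. Sleep, to which the other item in the ring sentence belongs, does enter the models as a factor of interest, so activity is the one left without a place.

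HRV is one of the two forms of the primary outcome in Aim 1. Hypothesis 1 concerns work-environment characteristics, and these include workload, shift type, shift length and overtime. Such features plausibly go together with how much a nurse walks in a day. If activity is related both to one of these factors and to HRV or reported stress, a coefficient estimated without it mixes the two associations. The same holds for the sleep factors of Hypothesis 2. The pilot is meant to inform a larger study, so an association that partly reflects activity could be carried forward as a work-environment or sleep finding.

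**Working it through.** The plan gives no figure on this point: no sample size, no effect size and no association between activity and any other variable. The main check is therefore a comparison of texts.

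**Where activity could appear**

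| Place | What is named | Activity named? |
|---|---|---|
| Aim 1 statement | a general promise, no variables | no |
| Aim 1 mixed models | age, sex, degree, two experience variables, smoking | no |
| Aim 1 equation, covariate term | sex, gender, race, age, mental health history, as examples | no |
| Aim 1 equation, factor term | job stressors and work environment | no |
| Aim 2 growth model | nurse and psychiatric characteristics | no |
| Aim 3 | age, sex, gender, race, psychiatric history | no |

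The mixed-model list is not introduced as a set of examples; the list under the equation is. The exact statement is therefore that no list names activity. It is not that adjustment is ruled out.

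**What omission could do (illustration on assumed values)**

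Work in standardised units and suppose that a factor F has no true effect on HRV. Let r be the correlation of F with activity and b the effect of activity on HRV. With activity omitted, the apparent slope of F is

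ρ = r × b.

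By the Fisher z approximation, the chance of a significant result at two-sided 0.05 with N nurses is

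1 − Φ(1.96 − m) + Φ(−1.96 − m), where m = ½ ln[(1 + ρ)/(1 − ρ)] × √(N − 3).

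The plan sets alpha at 0.05 without saying whether tests are one- or two-sided; two-sided is assumed here. The values of r, b and N are also assumptions.

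| r | b | ρ | N = 50 | N = 100 | N = 200 |
|---|---|---|---|---|---|
| 0 | any of 0.1, 0.3, 0.5 | 0 | 0.05 | 0.05 | 0.05 |
| 0.1 | 0.1 | 0.01 | 0.051 | 0.051 | 0.052 |
| 0.3 | 0.3 | 0.09 | 0.095 | 0.144 | 0.245 |
| 0.5 | 0.5 | 0.25 | 0.417 | 0.711 | 0.948 |

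With activity in the model, the rate returns to 0.05 under the same assumptions.

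Three limits apply. If r and b have opposite signs, ρ is negative, so omission can mask an association as well as create one. The relevant r and b are those left after the other covariates and sleep are accounted for, which the simple product ignores. And the calculation treats activity purely as a confounder; if it is a mediator, ρ is part of F's total effect and not a bias.

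**The case against.** The strongest reply is that the plan does not exclude activity. The covariates under the equation are examples only, and the general promise in Aim 1 is wide enough to cover steps/day. The mixed-model list is confined to personal characteristics and cannot be the whole set, since the equation's examples include gender, race and mental health history, which are not in it. The absence of an activity row in Table 1 proves little either: highest degree and tenure in the current setting are explicit covariates, and Table 1 has no row for them. All of this stands. A reader might infer that the plan leaves the confounder out of every model, or that HRV differences due to activity will be misattributed. The documents support neither statement.

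The second reply is causal. If workload or shift pattern changes how much a nurse walks, activity lies on the path from the factor to HRV, and adjusting for it removes part of the association that Hypothesis 1 is about. This also stands, and it is why neither the adjusted nor the unadjusted estimate should be shown alone.

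Two extensions are tempting and should be resisted. One is to adjust the Aim 2 growth model. Its outcome is the C-SSRS score, and the protocol calls activity a confounder for stress levels, not for suicidal ideation. The other is to adjust the Somni comparison for change in steps because the app displays them. A change in activity prompted by the app is part of what the intervention does, so this would condition on a post-intervention variable.

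What the reply does not remove is the gap between a named confounder and a model specification that is silent on it. If the promise is left open-ended, whether to include steps/day can be decided after the results are seen.

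**Conclusion.** The point holds for the Aim 1 models of self-reported stress and HRV. The protocol names activity as a confounder for stress, collects it, promises control for covariates of that kind, and then names it in no covariate list. Activity-related differences may therefore be read as work-environment or sleep associations.

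The textual omission is certain; the consequence is conditional. It requires activity to be related both to the factor and to the outcome, and neither association is given. The assumed cases above run from no practical effect to a serious one, and nothing in the documents says which applies or in which direction. This is a cheap improvement to a pilot analysis, not a defect that invalidates it.

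**What to change.** In the Aim 1 paragraph of the Statistical Analysis, add mean steps/day, averaged over the same window as the HRV value, as a covariate in the linear mixed models for self-reported stress and for HRV. Report each factor's estimate with and without it. State in advance that activity may partly mediate workload and shift effects, so that a difference between the two columns is not taken by itself as proof of confounding.

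Leave the Aim 2 C-SSRS growth model as it is on this point. In the Somni comparison, keep the main pre/post contrast unadjusted for change in steps and report the change in steps/day descriptively beside it.

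The data are already being collected. The cost is one degree of freedom per model, a second column of estimates and a few lines of SAP text.

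### Aim 3 models use of each sleep-kit item, but no described instrument records use of such items before the kit, so new use cannot be told from habit

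*Combined protocol and SAP*

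**What the plan says.** All references are to the combined protocol and SAP.

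- **Kit and app (Study Design, component 4).** The kit holds "Blue light blocking glasses, white noise machine, lavender spray, ear plugs, light blocking eye mask, and herbal tea". It comes with a "smartphone app that prompts participants to input the use of each component in the kit and provide a subjective sleep quality rating each day". Nurses decide for themselves how to use it: "participants are able to select their preferred use, timing, and duration of each of the box contents".
- **Comparison (same section).** Somni runs in Weeks 4 to 8, and its impact is to be judged "by comparing survey and physiologic metrics from Weeks 1-4". No control group is described, so each nurse's own earlier weeks are the reference.
- **Surveys (Study Design, component 1, and Table 1).** The surveys at baseline, Week 4 and Week 8 hold "demographic questions and validated measures for personal characteristics, sleep, stressful life events, psychiatric characteristics, work environment factors, and all psychological health outcomes". The Sleep row of Table 1 covers quality and duration and names the PSQI, the ring and Somni. No row asks about sleep aids.
- **Analysis (Statistical Analysis, Aim 3).** The plan will test differences in "use of sleep kit components at the individual level between the 3 data points". It also models "each *Somni*[®] sleep kit component (mean weekly frequency") as a predictor, adjusting for age, sex, gender, race and psychiatric history. There is no term for earlier use or for change in use.

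**The concern.** Ear plugs, an eye mask or herbal tea can be in a nurse's home before the study starts, and a nurse who sleeps by day after night shifts has an obvious reason to own them. If such a nurse carries on as before, her recorded use in Weeks 4-8 need not be a response to the kit.

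Two Aim 3 analyses depend on knowing this. The comparison of use over three time points needs values at baseline and Week 4. The item-level models ask which items go with better outcomes, and they read recorded frequency as exposure. If frequency mixes old habit with new use, an item that helps can look inert, and the ranking of items can reflect which goods were already common. This matters because the pilot is meant to inform a fully powered study, and item-level results are a natural input to that design.

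**Working it through.** The documents state no sample size, effect size or prevalence of earlier use, so there is no planned figure to reproduce. The check is a reading of the text, followed by an illustration with assumed shares.

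**1. What each analysis needs, and what is collected**

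| Analysis in Aim 3 | Data needed | Described source |
|---|---|---|
| Use compared over three data points | Use at baseline, Week 4, Week 8 | App, Weeks 4-8 only |
| Item frequency as predictor of outcome or growth | Frequency, with old and new use separable | App frequency only; no earlier value |

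Starting the app sooner would not clearly fill the gap. It prompts for components of the kit, so a nurse's own eye mask in Week 2 has no defined place in it. Nor do the documents contain a rule or instruction that keeps Weeks 1-4 free of such items.

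**2. How far an item's slope on change can move (illustration)**

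Assume that nurses log an item either daily or never, that habitual users log their use, that their use and outcome do not change, and that new daily users change by δ. Let q be the share of daily loggers who were already daily users.

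- Mean change among daily loggers = q × 0 + (1 − q) × δ = (1 − q)δ.
- Mean change among never-loggers = 0.
- Slope per day of use = (1 − q)δ / 7, against a true value of δ / 7. The ratio is 1 − q.

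Since q = habitual / (habitual + new), the result turns on the mix among loggers, not among all nurses:

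| Habitual daily users (assumed) | New daily users (assumed) | q | Slope retained |
|---|---|---|---|
| 10% | 30% | 10/40 = 25% | 75% |
| 10% | 10% | 10/20 = 50% | 50% |
| 30% | 10% | 30/40 = 75% | 25% |

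The same point can be made for one nurse. If she logs 5 days a week and u of them are old habit, the new share is (5 − u)/5, which runs from 100% at u = 0 to 0% at u = 5.

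**3. Where the illustration stops**

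- If habitual users do not log their own items, they sit among the never-loggers with zero change. On the same assumptions the slope on change is then not attenuated, but the zero-use group contains users.
- Where the outcome is a level, as in the model of mean C-SSRS, the 1 − q formula does not apply. Habitual users may differ in underlying sleep, so the bias is confounding and its sign is not known.

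**The case against.** **The protocol is short and does not show its surveys.** The planned three-point comparison of use, and the listing of Somni as a sleep measure in Table 1, suggest that the authors meant to have use data at all three points. That stands as intent. It does not supply an instrument before the kit arrives, and the stated intent makes the gap more specific.

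**This is a pragmatic pilot, and adding Somni to usual habits is a legitimate contrast.** This stands in full. A reader might infer that Weeks 1-4 are contaminated and that the overall Somni effect shrinks by the share of earlier users, for instance 10% to 50%. The documents do not support that. They never say that the comparison weeks are free of sleep aids. The percentages only restate an assumed prevalence for a single item. A nurse who already wore a mask still receives 6 − 1 = 5 other items, the app and its feedback graphs.

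**A habitual user is not necessarily recorded as a 7-day-a-week user.** A reader might assume that she is. The text does not say whether use of one's own items would be logged, so this too is an assumption.

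**In a level model, current frequency is the real exposure whatever its origin.** This is partly right, and the attenuation argument belongs to the models of change. It leaves confounding by long-standing sleep problems untouched, and the covariates listed for Aim 3 include neither earlier use nor shift type.

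**The aim is exploratory, and unchanged habit does not by itself create a false benefit in the before/after contrast.** This is correct, and it limits the weight of the point.

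**Conclusion.** The point holds for the item-level analyses. As described, the study has no pre-kit measure of use, so the three-point comparison of use cannot be carried out and the item models cannot distinguish habit from uptake. The size is unknown, because it depends on how common earlier use is, on how it differs by item, and on what nurses log. Earlier use itself is a plausible inference, not a documented fact; without a question, the study cannot learn whether the problem is large or trivial.

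The overall before/after contrast is not invalidated on this ground. It estimates the change when kit and app are added to usual habits, and reports should say so instead of implying kit versus no kit. I class this as a cheap improvement.

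**What to change.** 1. **Week 4 survey, completed before the kit is opened.** For each of the six item types, ask on how many of the past 7 days it was used, from any source. Repeat the identical items at Week 8. Asking first at Week 4, not at baseline, avoids prompting nurses to take up these items during the comparison weeks.
2. **Test of use.** Restate it as Week 4 versus Week 8 on that survey item. Do not subtract a recalled figure from the daily app log, since the two are different instruments. App frequency can stay as the description of use during Weeks 4-8.
3. **Item models in Aim 3.** Adjust for Week 4 pre-kit use of the item, or replace frequency with the Week 8 minus Week 4 change from the same survey item.
4. **Reporting.** Describe the overall contrast as Somni added to usual habits. Show the contrast in nurses with no earlier use of any item as descriptive only.

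The cost is six short questions in each of two surveys already being sent and one extra covariate per item model, which is not free in a pilot. The subgroup with no earlier use may be small. A 7-day recall at Week 4 also covers only the last part of the comparison weeks and has to stand for usual habit.

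### The 3-SD removal rule exempts no variable; if it is applied to the C-SSRS and ideation is uncommon, it deletes valid positive scores, highest first

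*Combined protocol and SAP*

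**What the plan says.** The opening paragraph of the Statistical Analysis section starts with composite scores for four groups of measures. It then lists summary statistics for normal, non-normal and categorical variables. The next sentence says that outliers and missing data will be assessed, and a parenthesis gives the action: "outliers > 3 standard deviations from the mean will be removed". The rule names no variable, exempts none, and does not say whether the single value or the whole nurse is dropped. No analysis with the removed values restored is described.

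The C-SSRS is the suicidal ideation measure in Table 1. Under Aim 2 the modelled outcome "is the C-SSRS score for nurse i at time t", and "we will fit conditional latent growth curve models using 3 data points". Under Aim 3 the plan adds: "We will repeat the same analysis modeling mean C-SSRS as the dependent variable". Neither place exempts the score from the rule.

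The Study Design section calls the study a "prospective pragmatic pilot trial to generate data needed to inform a fully-powered longitudinal study". Under Aim 1 the primary outcome is named as stress.

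**The concern.** A cutoff in standard deviations from the mean suits a roughly symmetric measurement in which a far value is probably a mistake. A suicidal ideation score may be zero for most respondents. The mean and SD are then small, and the values beyond the cutoff are the genuine reports of ideation.

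Removing them is selection on the outcome. The observed frequency and variance of ideation fall, and the nurses who carry most information about predictors of ideation lose their outcome data. At stake are Aim 2, the exploratory sleep-intervention aim, and the ideation figures that this pilot would hand to the larger study. With three survey waves it also matters whether one score or the whole nurse is removed.

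**Working it through.** **Inputs.** From the documents: the 3-SD cutoff, and the use of C-SSRS as a score with a mean. Not in the documents, and therefore assumed: the share p of nurses with a positive score, the score range (1-5 among positives), the distribution over that range, and the sample size. The plan has no figure of its own to reproduce.

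**Formula.** Let m be the mean and q the mean square of the score among positives. Then overall mean = pm and SD = √(pq − p²m²). A score s is removed if s > pm + 3·SD.

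**Below 10%, any distribution.** For a score between 0 and s with mean μ, the variance is at most μ(s − μ). The top score s is removed if (s − μ)² > 9 × variance. That is guaranteed if s − μ > 9μ, i.e. μ < s/10. Since μ ≤ ps, p < 10% is enough. For a yes/no score, z = √((1 − p)/p), which is 3.00 at p = 10% and 2.00 at p = 20%. In samples, using the n − 1 SD, all positives are removed if there are at most 4 of 50, 9 of 100 or 19 of 200, and none above that.

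**Above 10%, scores 1-5.** The top score sits exactly on the cutoff when (5 − pm)² = 9(pq − p²m²), i.e. 10m²p² − (10m + 9q)p + 25 = 0. The smaller root is the prevalence below which score 5 is removed:

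| Assumed scores among positives | m | q | Score 5 removed below |
|---|---|---|---|
| Half at 5, rest equal over 1-4 | 3.75 | 16.25 | 15.4% |
| Rising weights 1:2:3:4:5 | 3.67 | 15.0 | 16.8% |
| Uniform | 3.00 | 11.0 | 23.1% |
| Declining weights 5:4:3:2:1 | 2.33 | 7.0 | 38.1% |

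Steeper right skew than the last row raises the limit further.

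**Worked case: uniform scores, p = 10%.**
- Mean = 0.10 × 3 = 0.30. Variance = 0.10 × 11 − 0.30² = 1.01, so SD = 1.005.
- Cutoff = 0.30 + 3 × 1.005 = 3.31. All 4s and 5s go, which is 2 of 5 levels or 40% of positives.
- Each remaining level holds 2% of nurses, and 96% of values remain. New mean = 0.02 × (1 + 2 + 3)/0.96 = 0.125.
- New prevalence = 0.06/0.96 = 6.25%.
- New variance = 0.02 × (1 + 4 + 9)/0.96 − 0.125² = 0.276, which is 27% of 1.01.

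**Finite samples.** In one-wave simulations with n = 50 to 200 and the rule applied once, uniform and declining shapes lost 52-63% of positives at 5% prevalence, 31-43% at 10% and 12-16% at 20%. Top-heavy and rising shapes lost more at 5% (68-75%) but only 3-7% at 20%, where about 70-92% of samples lost nothing.

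**The case against.** The strongest reply is that the rule may not reach the C-SSRS at all. It could be limited to the composites that open the paragraph, "composite scores of individual measures (sleep, stressful life events, psychiatric characteristics, and work environment characteristics"), none of which is named as suicidal ideation. Or, because the cutoff is in SDs from the mean, it could be limited to variables summarised by mean and SD, which would leave out a mostly-zero score. Both readings are reasonable, and the second is good practice. Neither is written, however, and an analyst following the text has no stated ground to spare the C-SSRS. So it stands that coverage is a reading and not a certainty.

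It can also be said that outliers are to be assessed first. That is true, but the action attached is removal, with no condition that a value be wrong.

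The objection to a general prevalence threshold stands in full. A reader might infer that valid scores are lost whenever ideation is below about 20%. The table shows otherwise: the limit is 10% for yes/no scoring, below 20% for top-heavy or rising scores, and well above it for right-skewed ones.

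A reader might also infer that bias in the planned growth-curve estimates has been shown. It has not. Attenuation is what outcome selection of this kind would lead one to expect, but the planned model was not simulated, and in a small sample a coefficient can move either way.

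**Conclusion.** The point holds conditionally. As written, the plan permits the removal of valid C-SSRS scores and gives no protection against it. If the rule is applied to that score, the top score is beyond the population cutoff at any prevalence below 10%. Between 10% and roughly 40% the result depends on score shape. If ideation is common, the effect can be nil. In the worked case, 40% of positive scores are lost and about a quarter of the variance remains. These sizes rest on assumed prevalence, scoring and sample size.

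The consequence falls on Aim 2, the exploratory aim and the ideation planning values for the larger study. A reader might extend it to the trial's main result, but the documents do not support that: the primary outcome is stress, and no harm from the rule is shown there. The wording should be fixed before analysis.

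**What to change.** Add one sentence to the opening paragraph of the Statistical Analysis section:

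> No valid C-SSRS response will be removed for being extreme; only verified data-entry errors will be set to missing, at the level of the single value.

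This settles which reading applies to the C-SSRS and, for that score, whether a value or a nurse is dropped. It needs no new data. The cost is that extreme valid scores stay in the Aim 2 and exploratory models and may be influential. It does not cure sparse data: if few nurses report ideation, those models will remain poorly supported.
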